The postoperative care delivered to patients is on the 7th floor of the hospital, directly below the Labor and Delivery Unit. The same resident physicians and physicians staff this area.

5) Study Population

Pregnant women with high risk obstetric complications who present to Labor and Delivery at B-UMCT for care at time of delivery and/or to the clinic for a regularly scheduled visit will be potential individuals enrolled in our study.

Sample size calculations predict that with a wound breakdown rate of 20% in high risk patients, approximately 80 patients in each group would be needed to show a complication rate decrease to 5%. We will recruit a total of 200 patients, 100 in the control group and 100 in the study group.

When the women partake in the study device, they will no longer be pregnant as the device will be applied post operatively (after the cesarean section).

FORM: Application for Human Research		
NUMBER	FORM DATE	PAGE
F200	02/2014	8 of 14

6) Recruitment Methods and Consenting Process

Patients will be identified by the investigators during the course of their clinical work or by designated study personnel during pre-screening (see Appendix F). Patients eligible for inclusion in this study will be approached by the Principal investigator, Co-investigator, Senior Investigator, and/or study personnel if they meet the following criteria:

Inclusion criteria:

- 1) Maternal Age 18 or above
- 2) Cesarean delivery
- 3) Maternal condition which increases the risk of wound complication. These conditions include: Obesity (BMI >30), diabetes, HIV/AIDS, chorioamnionitis, rheumatologic disease, history of wound complication, anticoagulant therapy.
- 4) Patient able to read and speak English or Spanish (once the consent form has been approved, a translated Spanish consent will be submitted to the IRB for approval, no Spanish speaking patients will be recruited until approval is received)

Exclusion criteria:

- 1) Minors (<18 years of age)
- 2) Non-cesarean wound (ie tubal ligation wound)
- 3) No high risk maternal condition
- 4) Patient unable to read and speak English or Spanish.
- 5) Prisoners

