The PI and co-investigators will already be known to the patient per their clinical care and other non-clinical study staff will introduce themselves appropriately when presenting the research material. Please note: A Banner Employee will approach the subject first to ask them if they wish to learn more about the study, before any recruitment may take place. The consent document (see attached to this submission) will be used as an aid in discussing this research with patients. Though there is not script that the study personnel will read out to the patient, the sections of the consent form will be discussed with this patient before study proceedings are undertaken.

Additionally, patients who undergo a C-section when no study personnel are in the hospital may enroll via phone. Eligible patients who have been identified by a physician on Labor and Delivery will be asked if they would like to hear about the study. Those interested will discuss the study via phone with a member of the study staff on the VOTF using the phone disclosure as a guide. Patients will then be consented to the study in person, including access to PHI, by a member of the study staff before they leave the hospital.

We are requesting a partial PHI for recruitment purposes.

FORM: Application for Human Research		
NUMBER	FORM DATE	PAGE
F200	02/2014	9 of 14

7) Procedures involved in the Human Research

The randomization key will be provided by the department of statistics at the University of Arizona. Envelopes with a 1:1 study allocation (wound vac : no wound vac) will be provided and placed in the Pyxis on labor and delivery. The Pyxis is utilized for two reasons: 1) It is a standard place that the allocations can always be kept and 2) Nursing staff are required to access the Pyxis and an electronic log is kept of when the drawer was opened to retrieve an envelope with study allocation. This will provide adequate concealment of the allocations.

Once consent has been obtained from patients, an envelope containing the study allocation will be retrieved from the Pyxis.

- Non-wound vac patients will undergo wound closure with subcutaneous fat closure with Vicryl in all cases that this is practicable (in extremely thin patients, this may not be possible), followed by subcuticular skin closure also using Vicryl. A compression dressing will then be applied. This dressing is usually removed by the clinician the following day.

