- Wound vac patients will undergo wound closure with subcutaneous fat closure with Vicryl in all cases that this is practicable (in extremely thin patients, this may not be possible), followed by subcuticular skin closure also using Vicryl. The wound vac system will then be applied over the closed incision. This vac dressing will then be removed on the day of hospital discharge and replaced with a second bandage and the wound vacuum will be re-activated. The patient will remove both and discard on POD#7. This is per the manufacturer’s guidelines for length of use.
- If the patient fails the wound vac therapy- ie the wound separates and requires traditional wound care (packing, wet to dry dressing, etc), then the PICO system is no longer used as part of their care.

Essentially, the standard of care is to close the cesarean section incision. Different providers use different kinds of sutures (made of different material, and of different sizes) or staples to close the subcutaneous fat and the skin. Essentially what we are saying is that all patients in this study would have the subcutaneous fat and skin closed in the same manner (with Vicryl suture). To participate in the trial patients would have to agree to these closure materials - some patients would opt out of the study if they particularly wanted to have their skin closed with staples, for example (though I think that this would be rare as patients tend to prefer suture - it dissolves and does not have to be removed). We chose a standard closure with suture as there is evidence suggesting a lower rate of wound complications with suture as compared to staples.

We thought it would be unrealistic to try to standardize the entire operative approach (closure of the uterus, closure of the fascia) as the different providers working at the hospital may choose not to participate if the approach specified deviated too much from their usual technique.

FORM: Application for Human Research

NUMBER	FORM DATE	PAGE
F200	02/2014	10 of 14

8) Risks to subjects

The risks to subjects are minimal. All wounds will be closed in a way considered evidence-based. The only difference is the wound dressing applied over the closed wound and the time of removal. Though it is possible that the vac remaining over the wound may delay diagnosis of a wound complication this is very unlikely as the dressing is small, and a wound complication without significant surrounding erythema is uncommon.

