There is a small risk of loss of protected health information. The PI will mitigate this risk by keeping all consents in a locked cabinet and not keeping any patient identifiers with the data analysis documents.

9) Potential benefits to subjects and/or society

Patients will receive no monetary benefit from being in this study.

If the hypothesis of this study is correct, those in the treatment arm (ie the wound vac arm) may experience a lower rate of wound complications.

Wound management is a common clinical problem encountered in obstetrics. Implications of a lower complication rate with the utilization of wound vacs would include offering this treatment in high risk groups in the future.

10) Provisions to protect the privacy of subjects and the confidentiality of data

Privacy of subjects will be respected at all times during the study. Patients will only be consented in a private area (pre-operative area, clinic room or laboring room). Patients are asked during all encounters with a physician whether or not they would like their family or friends present. Patients will not be required to have support people leave the room for inclusion in the study.

Patient confidentiality will be respected at all times. The records review required for the study will only be performed by those personnel appearing on the VOTF. All documents with traceable patient data (ie consent forms/data collection forms) will be stored in a locked cabinet in the fellow’s office (Room 8327 G). These records will be stored for a period of 6 years.

A data sheet will be created to include all data pertaining to the study without any patient identifiers. This document will be kept separate from the consent forms and data collection forms.

Additionally, a REDCap database will be used to facilitate tracking patient follow-up and statistical analysis when study procedures are completed. The REDCap database will store identifiable information. The REDCap data base will be maintained for 6 years after completion of the study.

11) Access to Private Information

a. Authorization for Access to Protected Health Information

FORM: Application for Human Research

NUMBER	FORM DATE	PAGE
F200	02/2014	11 of 14

Patients agreeing to participate in this study will be made aware that record review of their protected health information will occur as a part of the study. The consent form includes a HIPPA consent.

b. Authorization for Access to Educational Information

N/A

12) Cost to subjects

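### For women enrolled by phone, no step is named as the consent that releases the allocation envelope, and the only consent described may come after the arm is visible

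*Protocol*

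**What the plan says.** All references are to Section 3 (Project Narrative) of the protocol.

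- **Item 7 (Procedures), the condition for allocation:** "Once consent has been obtained from patients, an envelope containing the study allocation will be retrieved from the Pyxis". No other condition is stated.
- **Item 7, timing of the dressings:** after skin closure, for controls, "A compression dressing will then be applied"; for the device arm, "The wound vac system will then be applied over the closed incision".
- **Item 6 (Recruitment and Consenting), the phone route:** "patients who undergo a C-section when no study personnel are in the hospital may enroll via phone". Interested women talk to a staff member by telephone with a phone disclosure as guide. After that they are to be "consented to the study in person, including access to PHI, by a member of the study staff before they leave the hospital".
- **Item 6, the general rule:** "the sections of the consent form will be discussed with this patient before study proceedings are undertaken".
- **Item 10 (Privacy), place of consent:** "Patients will only be consented in a private area (pre-operative area, clinic room or laboring room"). Item 4 says of the ward: "The postoperative care delivered to patients is on the 7th floor of the hospital, directly below the Labor and Delivery Unit".

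**The concern.** The phone route exists because no study staff are on site at the cesarean. In-person consent by study staff can therefore hardly be in place when the wound is dressed. Yet consent is what releases the envelope, and the envelope decides the dressing. The text names the telephone step a discussion and the later step consent, and it does not say which of the two item 7 means.

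The trial compares two dressings that look different and are removed at different times, so the woman knows her arm once she is dressed. If she is asked for consent and record access only then, her answer can depend on the arm she received. A refusal may take her outcome with it. That is selection after randomisation, which the 1:1 concealed allocation cannot protect against.

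**Working it through.** The point concerns the order of events, so the first check is textual.

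**Step 1. Possible orders for a phone-route woman.**

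| Order | Sequence | Conflict |
|---|---|---|
| A | phone discussion, draw, closure, dressing, in-person consent | The draw precedes the only step called consent (item 7; also the general rule in item 6) |
| B | phone discussion, closure, dressing, in-person consent, draw | The arm is drawn after the dressing is due (item 7, both arms) |

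Neither order satisfies every item as written. Item 6 also does not place the phone discussion before or after surgery.

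**Step 2. Which order is probably meant.** Three statements point to A:

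- Item 1 (Background) expects benefit from negative pressure started immediately after the operation.
- Item 2 (Lay Summary) has women randomised once they agree to take part.
- Item 7 requires participants to accept the closure materials, which makes sense only before closure.

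**Step 3. What order A implies.** In one arm, let *p* be the true complication rate, *f* the phone-route share, *r* the proportion of those women who refuse after being dressed, and *q* the complication rate among refusers. If refusers' outcomes are lost, the observed rate is

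(p − f·r·q) / (1 − f·r).

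It equals *p* only when f·r = 0 or q = p. Bias in the comparison depends on *f* and on *r* and *q* in each arm. The protocol gives none of these, so the bias has no calculable size.

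**Step 4. Whether plain loss of numbers matters.** Item 5 gives 20% against 5%, about 80 per group needed and 100 per group recruited. Alpha and power are not stated; I assume two-sided 5% and 80%. With mean rate 0.125:

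- √(2 × 0.125 × 0.875) = 0.4677 and √(0.20 × 0.80 + 0.05 × 0.95) = 0.4555.
- n = (1.960 × 0.4677 + 0.842 × 0.4555)² / 0.15² = 75.1, so 76 per group, or 88 with continuity correction. At 80 per group, power is 82.5% (normal approximation) or 79.3% (Fisher exact). The stated figure is plausible.
- Power at n per group = Φ[(0.15√n − 0.9167) / 0.4555]. At n = 100: Φ(0.5833 / 0.4555) = Φ(1.281) = 90.0%.
- Suppose *f* is 10% to 50% and *r* is 5% to 30%, both assumed. Then n = 100(1 − f·r) runs from about 100 down to 85. At n = 85: Φ((1.3829 − 0.9167) / 0.4555) = Φ(1.024) = 84.7%.

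Even the worst of these cases keeps more than the 80 per group that item 5 asks for. Loss of numbers is therefore not the problem. Selection after allocation is.

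**Step 5. Place of consent.** Item 10 lists three places, all before surgery or outpatient. In-person consent on the postoperative floor fits none of them. Item 6 does not say where that consent happens, so this is an inference and a small matter of alignment.

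**The case against.** **The natural two-step reading.** Enrolling by phone may well mean oral agreement before surgery that releases the envelope, with the in-person step only adding the signature and the health-information authorisation. The phone disclosure is not shown, and Section 4 lists a consent form and a research protocol as separate attachments, which may settle the matter. This stands to the extent that nobody should conclude from this text that women are randomised without having agreed. It does not remove the point. The text at hand assigns consent to the later step, and on this reading too the woman grants or withholds record access after seeing her dressing.

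**Withdrawal is allowed anyway.** Item 16 lets any woman leave at any time, and withdrawals can also differ by arm. True, but here every phone-route woman is asked afresh for consent and data access after allocation. An analysis plan can say how refusers are counted; it cannot supply outcomes that nobody was permitted to collect.

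**Stronger readings that the protocol does not support.**

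- A reader might infer dilution: women allocated to the device after a conventional dressing gain nothing, so the device-arm rate becomes 5% + 15% × share. At a 30% share that is 9.5%, and power at 100 per arm is 49% (Fisher) to 57% (chi-square). This needs order B, which fits items 1, 2 and 7 poorly, together with an invented share and zero benefit.
- A reader might infer that an early draw lets the operator know the arm during uterine and fascial closure. No item is contradicted by that, and fat and skin closure are the same in both arms.

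**Conclusion.** The conflict between items 6 and 7 is real and should be fixed. For women on the phone route, the protocol does not name the consent that permits allocation. On the most probable reading, the only consent it describes follows a visible allocation, so refusal can differ by arm and cost outcomes.

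Confidence is medium, because the phone disclosure and the separate research protocol were not available and the conclusion rests on reading order A as the intended one. The size is unknown, since neither the phone-route share nor any refusal rate is given. A loss of power should not be claimed.

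**What to change.** In items 6 and 7, state that:

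1. For the phone route, a documented phone consent is the consent that releases the envelope. It covers the closure materials and collection of outcome data, and is completed before skin closure (best before fat closure, since it covers those materials).
2. A woman without it at that point is not randomised.
3. The sealed envelope is opened only after cesarean delivery and completed skin closure, immediately before the dressing.
4. Every randomised woman is counted in her allocated arm, and any later refusal of the in-person signature is reported by arm.

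In item 10, add the place where in-person consent after surgery is taken.

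Naming in-person consent as the release step would also remove the conflict, but it would in practice end the phone route.

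The cost is protocol wording and opening the envelope at the end of surgery. Some phone-route women will not be randomised because phone consent was not documented in time. The IRB must accept that phone consent covers outcome data. If it does not, loss through later refusal remains possible, and reporting by arm will at least show it.

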
2) Lay Summary (approximately 400 words)

We aim to carry out a randomized controlled trial. Patients with a condition that increases their risk of a wound complication will be approached for inclusion in the trial. Each participant agreeing to study inclusion will be randomized to either suture alone or to closure of their skin incision with suture and then with prophylactic placement of a wound vac (PICO). The wound vac will be left in place until the day of discharge. Prior to discharge, the bandage will be removed, the wound inspected and a new bandage will be reapplied to the wound. The patient will remove the bandage and wound vacuum on POD#7 at home. Both items can be discarded in a normal trash receptacle. We will also obtain

FORM: Application for Human Research

NUMBER	FORM DATE	PAGE
F200	02/2014	7 of 14

permission to call the participants for a patient satisfaction questionnaire at 1 week post-op, and possibly 2 and 6 weeks if they have not presented for their post op/partum appointments or the questionnaire could not be obtained at their visit. The wound will be re-assessed at their 2 week and 6 week post-op follow up visits. The patients will be assessed by either the Principal Investigator, Co-investigator and/or Senior Investigator at their post-operative clinic visits. The investigator will ask the patient if they have had any postoperative complications since their surgery and will be asked to detail any complications if they answer yes to this question. They will also be asked to confirm that their wound has completely closed at this time.

3) Setting of the Human Research

Patients being approached for inclusion in this study are those presenting to labor and delivery for delivery care or to B-UMCT for their regularly scheduled clinic visit ([name]).

4) Resources available to conduct the Human Research

The Labor and Delivery unit at the Banner –University Medical Center comprises a triage area, up to 14 laboring rooms and 2 fully operational operating rooms.

There are 16 resident physicians, 2 clinical fellows and multiple OBGYN physicians available for the medical care of pregnant and laboring women. There is also around the clock nursing and anesthesia care available 7 days per week.

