Patients will not be charged for use of the wound vac. They will otherwise be billed for their hospital care.

13) Subject compensation

Subjects will not be compensated for participation in this study.

14) Medical care and compensation for injury

This study includes no more than minimal risk to subjects. If a patient has a complication during their hospitalization, their insurance will be billed for their care.

15) Monitoring the data for subject safety

N/A as this research poses no more than minimal risk to subjects.

16) Withdrawal of subjects

Patients may withdraw from this research at any time. If withdrawal occurs before vac placement, no additional interaction with an investigator will be needed. If withdrawal occurs after the vac has been placed, the physician caring for the patient will remove the vac as soon as practicably possible.

17) Sharing of results with subjects

Patients will not be contacted regarding the outcome of this research. If the outcomes are published at a later date, subjects will have access to overall results through this medium.

18) Information management

Information management will be the sole responsibility of the investigators. This will be carried out at the University of Arizona. The sponsoring company makes no stipulations regarding publication.

FORM: Application for Human Research

NUMBER	FORM DATE	PAGE
F200	02/2014	12 of 14

19) Drugs, Devices, and Gases

The wound vac (PICO system) is an FDA approved device for wound care. This is not an FDA trial.

20) Multi-site Human Research'

N/A

SECTION 4: LIST OF ATTACHMENTS FOR THIS SUBMISSION

Document Name	Version Date
1. Consent form	1. 8/22/16
2. Data Collection Form	2.
3. Research Protocol	3.
4. Appendix F	4. 8/22/16
5. Patient Satisfaction Questionnaire (for telephone interview)	5.
6. PICO patient information (Smith and Nephew brochure)- PDF	6.

Submission List for F200: Application for Human Research

Required items for all F200 submissions:

- F107: Verification of Training Form
- Current PI/Co-PI CVs or biosketch, if not included with copy of grant application

Other Items as applicable:

- **Biosafety Review letter** (for UA - Institutional Biosafety Committee)
- **Certificate of Confidentiality**
- **Compressed Gases Review letter** (for UA – Research Instrumentation)
- **Contract** – complete or draft copy of contract including budget

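### Consent is the only stated trigger for drawing the allocation envelope, so the arm may be known before surgery although it is not needed until the dressing

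*Protocol*

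**What the plan says.** All references are to the protocol, Section 3 (Project Narrative).

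- **Trigger for the draw** (item 7, Procedures): "Once consent has been obtained from patients, an envelope containing the study allocation will be retrieved from the Pyxis". No other event is named. The Lay Summary (item 2) says who is randomized, not when: "Each participant agreeing to study inclusion will be randomized".
- **Place of consent** (item 10, privacy): "Patients will only be consented in a private area (pre-operative area, clinic room or laboring room". All three places come before the operation on the standard route.
- **Phone route** (item 6, Recruitment): women operated on when no study staff are in the hospital may hear about the study by phone, with in-person consent at any time up to discharge.
- **When the arm is needed**: item 5 says "the device will be applied post operatively (after the cesarean section". Item 7 says, after describing closure, "The wound vac system will then be applied over the closed incision". The control dressing is likewise applied after closure. Item 8 gives the dressing and its removal time as the sole difference between arms.
- **What is standardized** (item 7): "all patients in this study would have the subcutaneous fat and skin closed in the same manner (with Vicryl suture". Fat closure is nevertheless done only where feasible.
- **What is not standardized** (item 7): "We thought it would be unrealistic to try to standardize the entire operative approach (closure of the uterus, closure of the fascia".
- **Withdrawal** (item 16): "If withdrawal occurs before vac placement, no additional interaction with an investigator will be needed".

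**The concern.** Randomization is best placed as late as the design allows, just before the point where treatment diverges. Here that point is the dressing, after the skin is closed. A draw tied only to consent can fall earlier, with two consequences.

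First, an operator who knows the arm before closing could, knowingly or not, close differently. Closure precedes the dressing and may affect the wound outcome. Pyxis storage with an access log protects the next allocation before it is drawn. It does not keep the operator unaware of the arm afterwards, and no shown text does so.

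Second, cesarean delivery is an inclusion criterion, yet women may be approached at a clinic visit or in labor. A consent-triggered draw permits allocating a woman who then delivers vaginally, or one who withdraws between the draw and the dressing. Either becomes a post-randomization problem that a later draw would mostly avoid.

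**Working it through.** **Step 1: order of events on the standard route.** Consent (pre-operative area, clinic or laboring room) comes first, then the operation, then fat and skin closure, then the dressing. The envelope may be drawn at any time after consent. The arm is first needed at the dressing. The whole operation therefore lies inside the interval in which the arm may be known without being needed.

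**Step 2: what the operator could vary.** Suture material for fat and skin is common to both arms. Left to judgement are whether fat closure is feasible and how the uterus and fascia are closed. The room for differential care is real but narrow.

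**Step 3: feasibility of a later draw.** Item 7 puts the envelopes in the Pyxis on labor and delivery, accessed by nursing staff. Item 4 puts both operating rooms in the same unit. Sample size and the 1:1 ratio are unaffected.

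**Step 4: illustration of a closure effect.** Inputs from item 5: 20% control rate, 5% target rate, 100 per arm. The affected share and risk change below are assumptions; the document gives neither.

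Shift in one arm = share of patients affected × change in their risk:
- low: 10% × 5 points = 0.5 points
- high: 20% × 10 points = 2 points

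The calculation is an exact binomial enumeration of the Pearson chi-square test without continuity correction, two-sided 5%, which is also an assumption. The rejection rate is the sum, over all tables with |z| > 1.96, of Bin(x; 100, p1) × Bin(y; 100, p2).

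| Shift (points) | No device effect: 20% v shifted device rate | Part favoring the device | Target effect: shifted control rate v 5% |
|---|---|---|---|
| 0 | 5.1% | 2.6% | 92.1% |
| 0.5 | 5.2% | 3.1% | 90.7% |
| 1 | 5.5% | 3.8% | 89.1% |
| 2 | 6.7% | 5.6% | 85.3% |

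Columns 2 and 3 suppose that early knowledge lowers the device-arm rate. Column 4 supposes that it lowers the control rate instead.

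**Step 5: illustration of losses.** Item 5 plans 100 per arm against about 80 needed, so 20 of 100, or 20%, may be lost before the stated requirement is breached. Power for 20% v 5% by the same method:

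| Evaluable per arm | Power |
|---|---|
| 100 | 92.1% |
| 95 | 90.7% |
| 90 | 89.0% |
| 80 | 84.9% |

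The document gives no frequency for non-cesarean delivery after consent or for withdrawal before the dressing. The planned margin covers moderate losses, so a later draw would mean fewer exclusions after randomization, not rescued power.

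**The case against.** The strongest reply is that the item 7 sentence sets an order, not a moment: no draw without consent. A draw after skin closure already complies with it, and retrieving an envelope is not opening it. That stands. A reader might infer that the protocol requires allocation at consent, or that operators will know the arm. The text supports neither; it leaves early knowledge open.

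Second, the route to bias is narrow. Fat and skin closure use the same suture in both arms, and the leeway for uterus and fascia is explained by differences between providers, not between arms. This also stands, and is why the point is minor.

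Third, the losses can be over-read. A reader might take item 16 to mean that a woman who withdraws early is dropped without outcome data. Read with the sentence that follows it, on removing a device already placed, it concerns whether further contact is needed. It does not say what happens to her data. Likewise, staff may in practice wait until a cesarean is certain, but nothing shown tells them to.

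Fourth, an envelope fetched at the end of every closure is a burden, and no text places the Pyxis inside an operating room. That is a fair cost, though a small one. Separately, a listed Research Protocol attachment is not shown and might describe envelope handling.

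**Conclusion.** The point holds as a cheap improvement, not as an error or contradiction. Consent is the only stated trigger, consent precedes surgery on the standard route, and the arms first differ at the dressing. The plan therefore permits early knowledge of the arm and some avoidable post-randomization losses without gaining anything from them.

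The likely effect is small and the document cannot size it. The false-positive and power figures rest on assumed shares, risk changes, losses and test. Even the upper assumption, one in five patients in an arm affected with a 10-point risk change, moves the two-sided error only from 5.1% to 6.7%. It would be wrong to conclude that the envelopes fail to conceal the next allocation, or that the trial would be underpowered for this reason.

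**What to change.** Replace the retrieval sentence in Section 3, item 7 with wording such as: *In a patient who has given consent, once cesarean delivery and skin closure are complete, nursing staff retrieve and open the next envelope from the Pyxis, and the assigned dressing is then applied.* Align the randomization sentence in the Lay Summary.

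The same edit must deal with the phone route; otherwise the new sentence conflicts with it. Item 6 allows in-person consent as late as discharge, after the dressing would normally be in place, and item 10 lists no postoperative place of consent. State which consent must precede allocation, and reconcile items 6 and 10 with that statement.

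Cost: a few sentences across items 2, 6, 7 and 10, an envelope fetched at the end of each closure, and a device at hand for each consented case. Sample size and allocation ratio do not change. The change does not blind care after the dressing or the outcome assessment, which the investigators carry out, and withdrawal after placement remains possible.
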